5.3 Secondary Endpoints

The following parameters are the secondary endpoints:

- **Response rate**
The response rates (complete response (CR), partial response (PR)) and overall response rate (CR or PR) are evaluated 4 weeks after the end of treatment.
- **Best response**

Best response is determined in the time interval from the start of therapy to end of follow-up

- **Time to best response**

Time to best response is defined as the time from the start of therapy to best response the patient achieves (CR, PR)

- **Time to first response**

Time to first response is defined as the time from the start of therapy to first response (CR, PR).

- **Progression free survival (PFS)**

Progression free survival (PFS) is defined as the time from registration to the first occurrence of progression or relapse as assessed by the investigator, or death from any cause. PFS for patients without disease progression, relapse, or death will be censored at the time of the last tumor assessment.

- **Time to treatment failure (TTF)**

Time to treatment failure (TTF) is defined as the time of registration to discontinuation of therapy for any reason including death from any cause, progression, toxicity or add-on of new anti-cancer therapy. Patients alive without treatment failure are censored at the latest tumor assessment date.

- **Duration of Response (DR)**

Duration of Response will be calculated in patients with response (CR, PR) to therapy from diagnosis of response to the date of progression, relapse or death from any cause. Patients alive without progression and relapse will be censored at the latest tumor assessment date or the stopping date.

- **Cause specific survival (CSS)**

Cause specific survival is defined as the period from the study registration to death from lymphoma or lymphoma related cause; death unrelated to MZL is considered as a competing event.

- **Overall survival (OS)**

Overall survival is defined as the period from the induction registration to death from any cause. Patients who have not died until the time of the analysis will be censored at their last contact date.

- **Quality of life during trial**

Quality of life will be measured by the FACT Lym (see Appendix I) before start of treatment and during trial participation.

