 - GFR calculation according to MDRD abbreviated formula
 - Quantitative immunoglobulins (IgG, IgA, and IgM)
 - Leukocyte immunophenotyping (FACS) PB and Bone Marrow Aspirate
 - Viral serology and detection
- Concomitant medication
- All women of childbearing potential will have a pregnancy test at screening

Once screening studies are complete and patient eligibility for this study is established, the provided inclusion checklist form will be completed for registration of the patient.

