Details for d): Time to first response is defined as the time from the start of therapy to first response (CR, PR). For calculation, the difference between the date of the first day of treatment in cycle 1 (*C1/D1*; see CTP pages 106-110) (variable *EXSTDAT* for *ACTIVITYID* = '*C1D1_SV*' in table **EX1**) and the date of first response (first date at which CR or PR is reached) will be used. For the determination, the variable *THERAPY_RESULT* (see section 'Details for b)' above) will be used, together with the date of assessment which is calculated as variable *ASS_DATE* from the variables *RSDAT_NMZEG*, *RSDAT_EGM* and *RSDAT_SMZ* in table **RS**. Patients who reach CR or PR: The earliest date at which CR or PR is documented will be determined for each patient across all points in time with tumor assessment and will be used as end date for time to first response (not censored). Patients who do not achieve the response category CR or PR, will be censored at the latest tumor assessment date.

Details for e): Progression free survival is defined as the time of registration to the first occurrence of progression or relapse as assessed by the investigator, or death from any cause. PFS for patients without disease progression, relapse, or death will be censored at the time of the last tumor assessment. Progression free survival will be calculated as difference between time of registration (date of patient signed written informed consent; variable *RFICDAT* in table **DM**) and the earliest date of the event (progression or relapse or death) or the date of last tumor assessment (in case of no event). For the earliest date in case of progression or relapse the dates in table **RS** will be used as follows: nodal MZL and extragastric MALT lymphoma: variable *RSDAT_NMZEG* for *RSORRES_NMZEG* = 4, extranodal gastric MALT lymphoma: variable *RSDAT_EGM* for *RSORRES_EGM* in (4 5), splenic MZL: variable *RSDAT_SMZ* for *RSORRES_SMZ* = 4. Additionally for the date of progression, the variable *RSDAT_ET* (table **DSET** IF *DSDECOD_ET* = 3) will be used for identifying patients with PD. For patients who died, the date of death will be determined using the variable *DTHDAT* in table **DSEOS**.

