Details for f): Time to treatment failure is defined as the time of registration to discontinuation of therapy for any reason including death from any cause, progression, toxicity or add-on of new anti-cancer therapy. Time to treatment failure will be calculated as difference between time of registration (date of patient signed written informed consent; variable *RFICDAT* in table *DM*) and the earliest date of the event (discontinuation of therapy for any reason). The following information will be used for the determination of the last mentioned date:

- discontinuation of therapy for any reason: variable *EXENDATE_ET* in table *DSET* for *DSDECOD_ET* not in (1 3).
- death from any cause: the date of death will be determined using the variable *DTHDAT* in table *DSEOS*
- progression: the dates in table *RS* will be used as follows: nodal MZL and extragastric MALT lymphoma: variable *RSDAT_NMZEG* for *RSORRES_NMZEG* = 4, extranodal gastric MALT lymphoma: variable *RSDAT_EGM* for *RSORRES_EGM* in (4 5), splenic MZL: variable *RSDAT_SMZ* for *RSORRES_SMZ* = 4. Additionally for the date of progression, the variable *RSDAT_ET* (table *DSET* for *DSDECOD_ET* = 3) will be used for identifying patients with PD.
- end of treatment: variable *RSDAT_ET* for *DSDECOD_ET* = 3 in table *DSET*
- death: variable *DTHDAT* for *DSDECOD_EST* = 4 in table *DSEOS*
- add-on of new anti-cancer therapy: variable *PRSTDAT* in table *PR2* for the first event in a patient

Patients alive without treatment failure are censored at the latest tumor assessment date.

Details for g): Duration of Response will be calculated in patients with response to therapy (CR, PR) from diagnosis of response to the date of progression, relapse or death from any cause. It will be calculated as difference between date of diagnosis of response and the earliest event date (progression, relapse or death from any cause). The date of diagnosis of response will be determined as variable *ASS_DAT* from the variables *RSDAT_NMZEG* (nodal MZL and extragastric MALT lymphoma), *RSDAT_EGM* (extranodal gastric MALT lymphoma) and *RSDAT_SMZ* (splenic MZL) in table *RS* for the variable *ACTIVITY_ID* = 'EOT_ASS' and *ASS_RESULT* in (1 2) (see section 'Details for a') above).

For the determination of the earliest event date, the following information will be used:

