- progression and relapse: For the date in case of progression or relapse the data in the tables *RS*, *DSET*, and *DSEOS* will be used as described in section 'Details for e)', see above
- death from any cause: For patients who died, the date of death will be determined using the variable *DTHDAT* in table *DSEOS*

In case of an event is the event date for remission duration the earliest date among these dates. Patients alive without progression and relapse will be censored at the latest tumor assessment date or the stopping date.

Details for h): Cause specific survival is defined as the period from the study registration to death from lymphoma or lymphoma related cause; death unrelated to MZL is considered as a competing event. CSS will be calculated as difference between time of registration (date of patient signed written informed consent; variable *RFICDAT* in table *DM*) and the date of an event (variable *DTHDAT* for *SURVSTAT* = 0 and *PRCDTH_DDORRES* = 1 in table *DSEOS*). Patients who have not died or died from another reason than lymphoma or lymphoma related cause until the time of the analysis will be censored at their last contact date.

Details for i): Overall survival is defined as the period from the registration to death from any cause. Overall survival will be calculated as difference between time of registration (date of patient signed written informed consent; variable *RFICDAT* in table *DM*) and the date of death (variable *DTHDAT*

for *SURVSTAT* = 0 in table *DSEOS*). Patients who have not died until the time of the analysis will be censored at their last contact date.

Details for j): Quality of life was measured by the FACT Lym before start of treatment and during trial participation. For statistical analysis, the FACT-Lymphoma Trial Outcome Index (TOI), the FACT-G total score, the FACT-Lymphoma total score and the sum score for each of the five subscales (physical well-being (PWB), social/family well-being (SWB), emotional well-being (EWB), functional well-being (FWB), lymphoma subscale (LYMS)), will be calculated. Details about the calculations are provided in two separate documents doc01_Administration Guidelines_Manual_082505.pdf and doc19_ScoringFACT-Lym v4-REVISED.pdf.

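### SAP 7.5 starts PFS, TTF, CSS and OS at the consent date although both documents define them from registration, which lengthens each time by an undeclared gap of 0 to nominally about 28 days

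*SAP*

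**What the plan says.** Protocol 5.3 takes registration as time zero for all four endpoints:

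- PFS: "Progression free survival (PFS) is defined as the time from registration to the first occurrence of progression or relapse".
- TTF: "Time to treatment failure (TTF) is defined as the time of registration to discontinuation of therapy for any reason".
- CSS: "Cause specific survival is defined as the period from the study registration to death from lymphoma or lymphoma related cause".
- OS: "Overall survival is defined as the period from the induction registration to death from any cause". The protocol describes no separate induction registration, and the SAP drops the word.

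SAP 7.5, details e), f), h) and i), repeats registration in each definition. It then equates registration with signed consent in each derivation and names RFICDAT in table DM as the start date. For PFS: "Progression free survival will be calculated as difference between time of registration (date of patient signed written informed consent". For TTF: "Time to treatment failure will be calculated as difference between time of registration (date of patient signed written informed consent". For CSS: "CSS will be calculated as difference between time of registration (date of patient signed written informed consent". The OS derivation uses the same variable.

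The protocol treats consent and registration as separate steps. Section 9.2 requires consent before any study-specific screening test. On registration it says: "Once screening studies are complete and patient eligibility for this study is established, the provided inclusion checklist form will be completed for registration". Section 10.2 requires both consent and fulfilled eligibility criteria for registration in the web-based system, and places registration before treatment starts.

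SAP section 3 lists the changes from the protocol and says that no others are known. The time origin is not on the list.

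**The concern.** Definition and derivation disagree within the same paragraph of the SAP, four times over. A table or curve labelled as time from registration would in fact show time from consent.

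The disagreement has a direction. The interval between consent and registration is spent in screening, and only patients who came through screening and were treated are analysed. It adds follow-up in which no analysed patient can have an event, so it lengthens event times and censored times alike. Because the sign is the same for every patient, the shift does not average out.

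At stake is the accuracy of four reported secondary endpoints. In a single-arm trial, readers are likely to set such curves beside outside results, so the stated time origin should be the one used.

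**Working it through.** The documents give no figure for the gap, so there is nothing to reproduce. The check is one of ordering, then bounds, then an illustration.

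**1. Order of dates.**

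- Consent precedes study-specific screening tests (Protocol 9.2). The flowchart in Appendix A puts it in the screening column, headed day -28.
- Screening tests fall within 28 days before C1D1 (Protocol 9.2).
- Registration follows completed screening and confirmed eligibility (Protocol 9.2, 10.2). SAP 2.1 gives the same order.
- Registration precedes first treatment (Protocol 10.2).

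Hence consent ≤ registration ≤ C1D1. SAP 2.1 also reports eight people who signed consent without meeting the inclusion criteria, beside 22 included. That confirms that consent and registration are different events here, but it says nothing about the gap in the 22.

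**2. Bounds on the gap g = registration − consent.**

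- Minimum: 0 days.
- Nominal maximum: 28 days, reached only if consent is signed at day -28 and registration falls at C1D1.
- 28/7 = 4.0 weeks; 28/30.4375 = 0.92 months.
- Over 22 patients, at most 22 × 28 = 616 patient-days, or 616/365.25 = 1.7 patient-years.

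**3. Events in the gap.** The Core Analysis Population (SAP section 4) holds eligible patients who received at least one cycle. None can have died or discontinued study therapy before registration. Disease growth during screening may be absorbed into the baseline, but it is not dated as a progression event. The shift is therefore never negative.

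**4. Illustration.** If every patient had the same gap g, the curve from consent would be the curve from registration moved right: S_consent(t) = S_reg(t − g). The table takes exponential curves, S_reg(t) = 2^(−t/m), with assumed medians m. The 14.2 months is the ibrutinib PFS cited in Protocol 4.3 and serves only as a reference value; the other medians are assumptions.

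| Assumed median m (months) | Rise in median, g = 28 d (0.92/m) | 12-month rate, g = 0 | g = 14 d | g = 28 d |
|---|---|---|---|---|
| 14.2 | 6.5% | 55.7% | 56.9% | 58.2% |
| 24 | 3.8% | 70.7% | 71.7% | 72.6% |
| 36 | 2.6% | 79.4% | 80.1% | 80.8% |
| 60 | 1.5% | 87.1% | 87.5% | 88.0% |

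At the nominal maximum, the 12-month rate rises by 0.9 to 2.6 percentage points. A 14-day gap gives about half of that.

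**5. Scale.** With 22 patients all followed for 12 months and a true rate of 55.7%, the standard error is √(0.557 × 0.443/22) = 0.106, or 10.6 percentage points. The largest shift in the table is about a quarter of that (2.6/10.6 = 0.25).

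**The case against.** The case for leaving this alone has several parts.

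- *The 28 days bound the wrong interval.* The window runs from screening tests to C1D1, not from consent to registration. Protocol 9.2 lets sites reuse recent standard-of-care results and older scans, endoscopies and marrow samples, and 10.2 asks for registration as soon as eligibility is met. Both point to shorter gaps. This stands: 28 days is a nominal maximum. It is not a strict one either, since the window limits tests and not the consent date.
- *Registration is not free of the same problem.* Analysed patients had to receive a cycle, so the interval from registration to C1D1 is also free of deaths by construction. This stands, but that interval belongs to the protocol's own definition, whereas the interval before it does not.
- *Nothing is hidden.* The SAP names the variable it uses. True, but the same sentences call that date registration, and section 3 declares no change.
- *It hardly matters.* SAP 8.2.3 treats the secondary results as hypothesis generating only. For PFS, scheduled imaging falls at C10D1 (9 × 21 = 189 days, or 27 weeks, after C1D1), at about 55 weeks, and then every 6 to 12 months, so a shift of 0 to 4 weeks is small against that spacing. This limits the importance of the point, not its correctness.

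A reader might also infer that starting PFS at consent and time to response at C1D1 is an SAP inconsistency. It is not: Protocol 5.3 itself starts time to best and first response at the start of therapy, and the SAP follows it.

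**Conclusion.** The derivations of PFS, TTF, CSS and OS in SAP 7.5 do not match the definitions in Protocol 5.3 or the SAP's own definitions, and the departure is not declared. Each time is too long by the patient's consent-to-registration gap: 0 to nominally about 28 days (0 to 0.92 months), always in the favourable direction. This rests on the order of steps in Protocol 9.2 and 10.2, on the 28-day window, and on an analysis set restricted to treated, eligible patients.

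A reader might infer that every patient gains four weeks, or that PFS is inflated by 6.5%. The documents do not support either. The typical gap is not given, and the percentage combines the nominal maximum with a background figure for another drug that no planned analysis uses as a comparator.

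Nor does the point touch the trial's main conclusion: the complete-response test against 56% uses none of these times. It is a small error in exploratory endpoints, worth correcting because the correction is cheap.

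**What to change.** In SAP 7.5 e), f), h) and i), replace RFICDAT with the actual registration date from the web-based system described in Protocol 10.2. SAP 7.7 makes the same substitution for study duration and should be aligned.

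The SAP names no registration-date variable, and the data items listed in Protocol 10.2 do not include the date, so it may have to be obtained from the registration system. If it cannot be brought into the database, use C1D1 (EXSTDAT in table EX1), which SAP 7.5 c) and d) already use. That is also not the protocol's origin, so SAP section 3 must declare it as a change from the protocol definition.

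The cost is a changed start date in four derivations, possibly one data request, and slightly shorter reported times. The primary analysis does not change.

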For the analysis of the overall response rate (CR or PR), a new variable *ORR* (yes/no) will be calculated from the variable *ASS_RESULT* as follows: IF *ASS_RESULT* in (1 2) THEN *ORR* = 1; ELSE *ORR* = 0;

Absolute and relative frequencies will be calculated for the statistical analysis of the variables *ASS_RESULT* and *ORR*.

Details for b): Best response (CR, PR, SD, PD) is determined in the time interval from the start of therapy to end of follow-up. At first, the single categories for the analysis of the response rates (CR, PR, SD, PD, NE) will be defined and calculated as described in section 'Details for a)' (see above) for each point in time in which a tumor assessment was performed and a new variable *THERAPY_RESULT* will be created. The best response for a patient is the minimum (i.e. the best outcome) of the variable *THERAPY_RESULT*, measured across all points in time with tumor assessment (over the entire observation time). The result is stored in a new variable *BEST_RESPONSE*.

Details for c): Time to best response is defined as the time from the start of therapy to best response the patient achieves (CR, PR). For calculation, the difference between the date of the first day of treatment in cycle 1 (*C1/D1*; see CTP pages 106-110) (variable *EXSTDAT* for *ACTIVITYID* = '*C1D1_SV*' in table **EX1**) and the date of best response (i.e. first date at which CR is reached; in case of no CR is reached, the first date at which PR is reached) will be used. For the determination, the variable *THERAPY_RESULT* (see section 'Details for b)' above) will be used, together with the date of assessment which is calculated as variable *ASS_DATE* from the variables *RSDAT_NMZEG*, *RSDAT_EGM* and *RSDAT_SMZ* in table **RS**. Patients who reach CR or PR: The earliest date at which CR or PR is documented will be determined for each patient across all points in time with tumor assessment and will be used as end date for time to best response (not censored). Patients who do not achieve the response category CR or PR, will be censored at the latest tumor assessment date.

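### SAP 7.5 starts duration of response only at the EOT assessment and dates best response by the first response, so neither matches its own definition

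*SAP*

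**What the plan says.** **Duration of response.** Protocol 5.3 runs DR in patients with CR or PR "from diagnosis of response to the date of progression, relapse or death from any cause". SAP 7.5 g) opens the same way: "Duration of Response will be calculated in patients with response to therapy (CR, PR) from diagnosis of response to the date of progression". The derivation that follows then takes the response date from table RS "for the variable *ACTIVITY_ID* = 'EOT_ASS' and *ASS_RESULT* in (1 2", the codes 1 and 2 being CR and PR. Only the EOT assessment can supply a start date.

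**Time to best response.** Protocol 5.3: "Time to best response is defined as the time from the start of therapy to best response the patient achieves (CR, PR". SAP 7.5 c) first spells this out as "first date at which CR is reached; in case of no CR is reached, the first date at which PR is reached". Its later instruction on the end date reads: "The earliest date at which CR or PR is documented will be determined for each patient across all points in time with tumor assessment". Apart from the endpoint's name, that instruction is the one given in 7.5 d) for time to first response.

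**Cause-specific survival (CSS).** Protocol 5.3 and SAP 7.5 h) both treat a death unrelated to MZL as a competing event. SAP 7.5 h) then says: "Patients who have not died or died from another reason than lymphoma or lymphoma related cause until the time of the analysis will be censored". SAP 8.2.3 specifies only Kaplan-Meier plots for this endpoint.

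SAP section 3 lists the changes from the protocol and states that no others are known. None of these three points is listed.

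**The concern.** Response is assessed at C10D1 and in follow-up as well as at EOT (Protocol 9.1.2, 9.3, 9.5 and Appendix A), and SAP 7.5 b), c) and d) use every assessment. Tying DR to EOT alone makes it conditional on being in response at EOT. That removes the shortest responses, those gained by C10D1 and lost before EOT, and it cuts the early part off every response that lasts. The Kaplan-Meier curve would then describe a different quantity from the one named.

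If the end-date instruction in 7.5 c) is programmed as written, time to best response duplicates time to first response. It then says nothing about PR deepening to CR, although CR is the primary outcome. The protocol expects such deepening: Appendix D classes an otherwise complete response as PR when marrow involvement persists or marrow was not re-examined, and 9.1.3 foresees a later marrow examination to confirm CR.

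For CSS, censoring competing deaths and reading one minus the Kaplan-Meier curve as a risk overstates the cumulative incidence of lymphoma death whenever such deaths occur.

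**Working it through.** The documents give no DR or time-to-best-response figure to reproduce, so the check sets each definition against its derivation and works out the timing from the visit schedule.

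**Schedule (days from C1D1)**
- Cycle length is 21 days (Protocol 6.1). 18 × 21 = 378 days = 54 weeks, which matches 6.1.
- C10D1 = 9 × 21 = 189.
- EOT is 4 weeks after C18D1 (Protocol 9.4): 17 × 21 + 28 = 385.
- Gap = 385 − 189 = 196 days = 28 weeks = 196 / 30.4375 = 6.44 months. Counted forward from C10D1 it is the same: 8 × 21 + 28 = 196.
- Protocol 9.3 also places the C10D1 visit 4 to 6 weeks after C9D1, which is day 168 + 28 = 196 to 168 + 42 = 210. If later cycles run from that visit, the gap is still 196 days. If C18 keeps its nominal date, the gap is 385 − 196 = 189 down to 385 − 210 = 175 days.

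**Both rules applied to four illustrative patients**

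| Course (assumed) | Time to first response | Time to best response: definition / end-date instruction | DR: definition / derivation |
|---|---|---|---|
| A: PR at C10D1, CR at EOT, PD day 900 | 189 | 385 / 189 | 900 − 189 = 711 / 900 − 385 = 515 |
| B: CR at C10D1, PD day 300 | 189 | 189 / 189 | 300 − 189 = 111 / no record |
| C: SD at C10D1 and EOT, first PR day 567, PD day 1100 | 567 | 567 / 567 | 1100 − 567 = 533 / no record |
| D: CR at C10D1 and EOT, PD day 900 | 189 | 189 / 189 | 711 / 515 |

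Under the end-date instruction, time to best response equals time to first response in every row. It departs from the definition wherever PR precedes CR (A). DR is 196 days short for continuing responders (A, D) and absent for B and C, although 7.5 b) counts both as responders.

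**Share of C10D1 responders lost from DR**

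Assume DR from C10D1 is exponential with median *m* months. The share failing before EOT is 1 − 2^(−gap/*m*).

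| Assumed median (months) | Gap 6.44 months (196 days) | Gap 5.75 months (175 days) |
|---|---|---|
| 12 | 31.1% | 28.3% |
| 24 | 17.0% | 15.3% |
| 36 | 11.7% | 10.5% |

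The medians are assumptions; the documents give none for this regimen in MZL.

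**CSS.** No arithmetic applies. The same paragraph of 7.5 h) names unrelated death a competing event and then censors it, and 8.2.3 offers no estimator that handles competing events.

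**The case against.** - **DR can be read as anchored at EOT.** Protocol 5.3 evaluates response rates 4 weeks after the end of treatment, the DR text does not say first diagnosis, and 7.5 g) refers back to the EOT categories in 7.5 a). Even so, an EOT anchor would be an undisclosed restriction. It still drops patients whom the SAP itself counts as responders, so this does not rescue the derivation.
- **Part c) is an inconsistency, since the correct rule is also there.** This is true. The calculation sentence is right and only the later end-date instruction is wrong. But that instruction is the operative one, and two programmers could produce different results and both cite the SAP.
- **The 196 days are nominal.** They apply to patients still in response at EOT. They hold if cycles after C10D1 keep to 21 days, and otherwise fall to 175 to 189.
- **Gastric MALT.** Appendix E requires two consecutive negative investigations for CR, so a confirmed CR at C10D1 may not be possible there. A PR would still start DR.
- **Coding of early-termination visits is not stated.** Appendix A shares one column for EOT and early termination. If both are coded EOT_ASS, a patient who stops early while in response keeps a DR record. One with PD at that visit is still lost.
- **Consequences are limited.** SAP 8.2.3 calls these results hypothesis generating, PFS captures every early progression, and best response captures every response. This limits the severity and leaves the error in place.

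**Conclusion.** The concern holds. As written, DR excludes C10D1 responders who fail before EOT and patients who first respond after EOT, and it starts 196 days late on the nominal schedule for C10D1 responders still in response. The expected loss of 17% (12% to 31%) of C10D1 responders rests on the assumed exponential medians of 24 (36 to 12) months; the 196 days rest only on the visit schedule. The net bias in DR has no fixed sign, because dropping early failures lengthens it and the late start shortens it.

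The end-date instruction for time to best response contradicts the definition just before it, by 196 days for PR at C10D1 and CR at EOT. No patient is lost from that endpoint. The CSS mismatch is real but the smallest of the three.

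The primary analysis is unaffected. With 22 patients enrolled (SAP 2.1), one or two misplaced responders would visibly change the curves, so the derivations should be corrected.

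**What to change.** - **7.5 g):** set the DR start to the first ASS_DATE with THERAPY_RESULT in (1 2) at any assessment, the date already derived in d), for every patient with any CR or PR. If DR from EOT is also wanted, report it separately under its own name.
- **7.5 c):** replace the end-date instruction with the first ASS_DATE at which THERAPY_RESULT equals BEST_RESPONSE, where BEST_RESPONSE is 1 or 2. Leave the censoring of patients without CR or PR as it is.
- **7.5 h) and 8.2.3:** report lymphoma death by Aalen-Johansen cumulative incidence, with unrelated death as the competing event.

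The cost is SAP wording and programming. No new data are needed, and the response variables and dates are ones the SAP already derives.
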